### 5. Inclusion/Exclusion Criteria

We will recruit 15 total participants with clinically-definite and genetically-confirmed Kabuki syndrome type 1 age 18 years and older. Clinical diagnosis of KS will be made based on recently published consensus diagnosis criteria. Genetic confirmation of a pathogenic mutation in *KMT2D* will also be required. Exclusion of participants younger than 18 years old is based on: 1) adults being able to consent to their own diet therapy, 2) ability to adhere to the diet, and 3) ability to standardize one cognitive battery to compare across and between participants. Other exclusion criteria include presence of another known genetic syndrome, a health problem that would make a modified Atkins diet harmful, inability to travel to Baltimore for 2 visits separated by 12 weeks. Recruitment of participants will be done solely by asking adults already participating in IRB00240569 to participate in this study as well. No recruitment will be done of participants not already enrolled in the other study.

#### 6. Drugs/ Substances/ Devices

a. The [name] lab demonstrated in 2016 that neurogenesis and memory deficits in the mouse model of KS was not only rescued by administration of HDAC inhibitor AR-42, but that it was also rescued with the ketogenic diet (Figure 2). Beta hydroxybutyrate, a ketone body that is actively transported into the central nervous system and enters the hippocampus during ketosis, is a potent HDAC inhibitor. Modified Atkins diet (MAD) has been shown to be an effective, safer to initiate, and easier to comply with substitute for the ketogenic diet in other CNS processes like epilepsy. Thus we believe the rationale is there to attempt a low-risk pilot study using this intervention in patients with KS. The Neurology teams at Johns Hopkins include nutritionists, clinicians, and researchers who have extensive experience with MAD and they will be available for consultation and for any diet-related needs. 12 weeks was chosen because that is the minimum amount of time used to see effect in studies on the ketogenic diet or MAD. Additionally, 8 weeks is the approximate length of time of neurogenesis of a new neuron. Since we suspect neurogenesis plays a role in cognitive performance in KS, the 12 week duration allows for neurogenesis to take place. To date, no study of treating epilepsy in KS with ketogenic diet or MAD exists. AR42 and Vafidemstat were chosen as in vitro comparisons (no in vivo use of these drugs) because of the previous evidence from the [name] lab that

both HDAC inhibition and LSD1 inhibition also ameliorate the phenotype in mice like ketogenic diet does.

### 7. Study Statistics

- a. Primary outcome variable: Change in cognitive testing protocol before and after 12 weeks of the diet
- b. Secondary outcome variables: 1) Change in anxiety measure scores after 12 weeks on the diet. 2) Change in genome-wide DNA methylation array signature while on the diet.
- c. Statistical plan including sample size justification: We will recruit 15 participants to this study with a goal of having 10 participants who complete the whole 12 weeks. We will only analyze data from participants who complete the whole 12 weeks. This number is completely generated based on the rarity of the disease model and therefore how many participants were felt were feasible to recruit. This is a very early stage, non-masked trial with no control group so no power analysis was done. To analyze the data, we will do intra-subject comparisons of the testing measures before and after 12 weeks of the diet, controlling for practice effects and for the fact the cognitive assessment protocol will be repeated 3 times in these participants. We will perform regression analysis to determine if the change is dependent on BHB levels. We will investigate whether scores on a measure of anxiety and if genome-wide DNA methylation analyses change after 12 weeks of diet and also if these potential changes moderate any change seen on cognitive assessment protocol.
- d. Participants will only stop early based on inability to tolerate the diet. With only 15 participants, there will be no interim data analysis to stop early.

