### 2. Objectives

Objective 1: Test whether HDAC inhibition through modified Atkins diet modifies the neurocognitive or neurobehavioral phenotype in individuals with Kabuki syndrome. Previously, a ketogenic diet has been shown to ameliorate cognitive and neurohistological defects in a mouse model of Kabuki syndrome. This proposal aims to conduct a pilot study of 10-15 adult patients with Kabuki syndrome given 12 weeks of HDAC inhibition through diet and determine whether performance on the cognitive assessment protocol changes.

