The study flow is outlined in Figure 1. These consented adult participants will participate in an initial study visit. These participants will undergo cognitive and neurobehavioral testing and also will have baseline labs drawn and will meet with a study team member trained in modified Atkins diet for education. The labs are standard of care for diet initiation to rule out contraindications (CBC, CMP, lipids, UA, urine amino acids, free and total carnitine, Vitamin D, selenium). Blood will also be taken for genome-wide DNA methylation analysis to look for the known abnormal signature in Kabuki syndrome and see if it changes over time with the diet. Participants and/or their caregivers will keep a daily diet log and/or will be asked to download the free Carb Manager application onto their smartphone. They will send the logs and data back weekly. The application is optional, only if participants prefer it to keeping their own logs. Participants will be given urine ketone strips and asked to use and record in their diet log twice weekly. Participants will have blood ordered and drawn remotely every 3 weeks and sent securely to the study team. Beta-hydroxybutyrate will be measured on this sample as well as genome-wide DNA methylation measured every 3 weeks to see if it changes over the course of the trial. At the 6 week mark participants will also securely send a urine sample for measurement of urine ketones and amino acids to investigate metabolism while on the diet. Participants will return to Baltimore at the end of 12 weeks for a one day visit to repeat the cognitive assessment protocol, neurobehavioral measures, and repeat the initial lab tests including genome-wide DNA methylation (Figure 1).

- b. The study will last for 12 weeks for each participant. There will be 2 on site study visits. Participants will then return home for the 12 week diet. They then will return to Baltimore for a 1 day study visit.
- c. This study is not blinded for participants or investigators because that would be too difficult logistically since the participants have to keep the diet. Additionally, because this is just a very small pilot study, blinding is not necessary.
- d. Participants will receive all standard of care and treatments. None will be stopped.
- e. No placebo group will be used because this is only a pilot study and placebo groups will come in later studies.

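### The primary outcome names a whole cognitive battery (nine listed instruments) but no primary score, and the BHB regression and moderation analyses inherit the gap

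*Combined protocol and SAP*

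**What the plan says.** Section 7, item a gives the primary outcome in one line: "Primary outcome variable: Change in cognitive testing protocol before and after 12 weeks of the diet". The objective in section 2 is equally broad: the study is to "determine whether performance on the cognitive assessment protocol changes".

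Table 1 lists nine instruments under the Cognitive Assessment Protocol and ranks none of them: Benton line orientation, Brief Visuospatial Memory, Picture Story Memory, Wechsler verbal, Beery visual motor integration, Beery visual perception, Flanker, Card Sorting and Block Design. They cover seven areas, including language and executive function. The Hopkins verbal test sits in a separate row group.

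For the analysis, item c says "we will do intra-subject comparisons of the testing measures before and after 12 weeks of the diet". The adjustment it names is for repetition: "controlling for practice effects and for the fact the cognitive assessment protocol will be repeated 3 times in these participants". It names none for the number of tests. It then adds "We will perform regression analysis to determine if the change is dependent on BHB levels", and asks whether changes in anxiety and methylation occur and "if these potential changes moderate any change seen on cognitive assessment protocol".

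On design, item c says "This is a very early stage, non-masked trial with no control group so no power analysis was done", and section 4, item e says "No placebo group will be used because this is only a pilot study".

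**The concern.** A primary outcome is useful because it fixes, before the data are seen, the number by which the study will be read. Here the label is present and the number is not. Section 3 gives a clear scientific target, visuospatial reasoning and memory linked to the dentate gyrus, but section 7 does not carry it forward. As written, a change in a language or executive test bears on the primary outcome as much as a change in the visuospatial tests that motivate the study.

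The gap spreads. The BHB regression and the moderation analyses both take the cognitive change as their outcome, so each can be run on any of the instruments.

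Section 3 says the pilot could lead to a larger trial. If the largest of several noisy changes in about 10 people became the headline, the later trial could be planned around an effect that is too large. With no control group, and with the practice adjustment named but not described, fixing the score in advance is one of the few safeguards available.

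**Working it through.** **The plan's own figure.** Ten completers with about 30% dropout need 10 / (1 − 0.30) = 14.3, rounded up to 15. This matches the stated recruitment of 15. The documents give no alpha, power, effect size or SD, so there is no error rate to reproduce.

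**Inputs from the documents.** 10 completers (section 7, item c; section 4, item a) and nine instruments, counted from Table 1.

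**Assumptions not in the documents.** No true effect, no practice gain, normal change scores with equal SD, and a common correlation ρ among the nine change scores of 0, 0.3, 0.5 or 0.7. The false-gain calculation also assumes paired t-tests at two-sided 5%, that is 2.5% in the direction of gain.

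**1. Size of the largest change.** The part of the change shared by all tests averages zero and does not affect which test comes out on top. The expected maximum of nine independent standard normal values is 1.485, so the expected largest mean change is 1.485 × √((1 − ρ)/10), in SD of change:
- ρ = 0: 1.485 × √0.100 = 0.47
- ρ = 0.3: 1.485 × √0.070 = 0.39
- ρ = 0.5: 1.485 × √0.050 = 0.33
- ρ = 0.7: 1.485 × √0.030 = 0.26

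For one score fixed in advance the expected value is 0. Simulation gave the same values. This step needs no alpha.

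**2. Chance of at least one false gain.** With independent tests, 1 − 0.975⁹ = 0.204. Simulation with n = 10 gave 0.204, 0.172, 0.145 and 0.110 at ρ = 0, 0.3, 0.5 and 0.7, against 0.025 for one score.

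**3. Sensitivity to the count.** With independent tests, counting the seven areas gives 1 − 0.975⁷ = 0.162. Counting ten tests, with Hopkins added, gives 1 − 0.975¹⁰ = 0.224. The finding does not depend on the count being exactly nine.

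**4. BHB regression.** With n = 10 and no true association, the largest of nine absolute correlations averages 0.59, 0.57, 0.55 and 0.50 at the same values of ρ (simulation). A single score averages 0.27.

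**The case against.** The strongest reply is that this is a small, uncontrolled pilot with no power analysis, and Table 1 gives outcome measure development as the purpose of the battery. Reporting a whole battery is reasonable in that setting, and formal error control matters less. This stands: it limits the seriousness of the point and is why an exploratory label is an acceptable remedy. It does not supply a primary score, and item a still declares a primary outcome.

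A reader might infer that the plan allows any single gain to be presented as the primary result, or that the investigators mean to choose the best one. The documents do not support this. As worded, the outcome is change in the protocol as a whole, so one test's gain is not that outcome. The plan is vague rather than permissive, and nothing in it shows an intention to select.

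A reader might also take the 20% to 11% as the trial's error rate. It is not: the plan states no alpha and describes no decision rule.

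The number nine is a count from Table 1, not a stated figure. It assumes that item a's testing protocol is the Cognitive Assessment Protocol, which is the likely reading. Wechsler verbal is not broken down, so there may be more scores.

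Finally, naming one score would not remove practice gain. That is correct, and it is a separate issue.

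**Conclusion.** The point holds as a gap in definition that should be closed. Section 7 declares a primary outcome without identifying a score. Following item c as written gives nine unranked comparisons with no adjustment for their number, and the BHB and moderation analyses rest on the same undefined change. No other section fills the gap.

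If the largest change were headlined under no true effect, it would average 0.47 to 0.26 SD of change for ρ from 0 to 0.7. If tests were run at two-sided 5%, a false gain on at least one instrument would occur in 20% to 11% of studies, against 2.5% for one score. These sizes rest on 10 completers, equal correlations and no practice gain. They show what the open definition could cost; they do not predict what this study will report.

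**What to change.** Before Week 12 data are analysed, make one of two changes.

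**Name a primary score.** Amend item a to name one visuospatial score, in line with section 3. It may be a single test, or a composite whose component scores, scaling and rule for a missing component are fixed in advance. Word the objective in section 2 to match. Use the same score in the BHB regression and the moderation analyses, and report its change with a 95% confidence interval. Report all other battery scores, including the individual components of any composite, as secondary or exploratory with 95% confidence intervals, and rest no headline claim on any of them.

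**Or declare the battery exploratory.** State in item a that there is no single primary score, that every test will be reported with a confidence interval, and that no efficacy claim will rest on any one test or any one BHB regression.

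Entry is staggered and the investigators are not blinded, so record the date of the choice and whether any Week 12 results had been seen by then.

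**Cost.** Both options change wording only, because the tests are already collected. Under the first, a benefit confined to a test outside the primary score becomes exploratory, and a composite may gain or lose power depending on how many of its components respond. Under the second, the study gives up a primary result. Neither deals with practice gain, for which item c still needs a stated method.

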# 4. Study Procedures

a. Participants with Kabuki syndrome 18 years and older will be recruited to participate. Recruitment will stop once fifteen participants are consented. This number allows for the ~30% rate of dropout expected based on difficulty complying with the diet in order to have data from 10 participants. Exclusion criteria would be inability to tolerate or comply with modified Atkins diet, inability to do repeat blood and urine testing, and inability to travel to Baltimore for 2 study visits 3 months apart. Participants will begin whenever they have their initial visit and conclude 12 weeks later. See Figure 1.

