- f. If participants cannot tolerate and/or adhere to the diet during the 12 weeks by their own self report and diet logs, they will be removed from the study.
- g. Participants can go back to their typical diet after the study ends or if they end the study early.
- h. Participants will have blood drawn 5 times and urine collected 2 times. Blood and urine collection at the initial and final study visits will be done at KKI. Most of the blood and urine will be sent to JHH core lab and are standard of care for diet

initiation and monitoring to rule out contraindications or severe side effects (CBC, CMP, lipids, UA, urine amino acids, free and total carnitine, Vitamin D, selenium). Another 2 purple top tubes of blood will also be taken and transported to the [name] lab by a study team member to run a genome-wide DNA methylation array to look for the known abnormal signature in Kabuki syndrome and see if it changes over time with the diet. The total additional blood volume taken beyond the standard of care labs for the diet will be 6 mL. In addition, participants will have blood ordered and drawn remotely every 3 weeks and sent securely to the study team. Once the study team receives it, one vial will go to JHH core lab and one to the [name] lab. Beta-hydroxybutyrate will be measured on this sample by JHH core lab every 3 weeks and the other tube will again be taken to the [name] lab to perform genome-wide DNA methylation arrays at 6 weeks to see if it changes over the course of the trial.

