# 8. Risks

a. The main risk of this study is the modified Atkins diet. Potential risks of the diet include kidney stones, constipation, acidosis, diminished growth, weight loss, and hyperlipidemia. The rest of the proposed research presents no more than minimal physical, psychological, legal, or financial risk to participants. Neurological examination is part of a routine physical examination and involves no more than minimal risk to the participants. Neuropsychological testing can take a prolonged amount of time and can cause anxiety and discomfort in participants. Venipuncture can cause discomfort and mild bruising or bleeding at the site. Risk of infection is minimal. Patients may be disturbed by seeing their blood drawn. Risk of using the CarbManager application is minimal. Participants do not enter name or date of birth. They do enter a username (which will be their subject ID), sex, and year of birth. However sex and year of birth can be skipped. Other than that, participants only enter diet logs daily. The participant then generates weekly reports through the app that will be saved as a pdf to their device which they then will securely email to the study team. Use of the app is optional for participants and they can opt to just type their diet logs and securely email them

- b. Labs and an exam will be done at the initial study visit to ensure that participants are healthy enough for 12 weeks of diet. Additionally, participants will be thoroughly educated about the diet at their initial study visit including potential adverse effects. Weekly check-ins with participants will be done to ensure they are complying with the diet and hear about any adverse effects. Subjects will be allowed to take breaks during Neuropsychological testing if significant anxiety or discomfort occurs. We will reinforce at each study visit that subjects can stop study procedures at any time if needed.
- c. Any problems should be reported directly to [name] and she will be responsible for reporting the adverse events and responding to them. This study does have a DSMB consisting of 4 JHH faculty members.

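### The removal and stopping rules (section 4 item f, section 7 item d) give no ground for withdrawing a participant on a lab or other safety finding, although the protocol draws labs for that purpose

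*Combined protocol and SAP*

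**What the plan says.** All references are to the combined protocol and SAP.

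- **Why labs are drawn.** The study-flow text in section 4 says of the initial-visit tests: "The labs are standard of care for diet initiation to rule out contraindications". Section 4, item h describes the clinical labs as standard of care for diet "initiation and monitoring to rule out contraindications or severe side effects". Section 8, item b says: "Labs and an exam will be done at the initial study visit to ensure that participants are healthy enough for 12 weeks of diet".
- **Who should not be on the diet.** Section 5 excludes people with a health problem for which the diet would be harmful.
- **Who is removed.** Section 4, item f opens: "If participants cannot tolerate and/or adhere to the diet during the 12 weeks by their own self report and diet logs". Such participants are taken out of the study.
- **Who stops early.** Section 7, item d: "Participants will only stop early based on inability to tolerate the diet".
- **Other safeguards.** Section 8 provides weekly check-ins, freedom to stop study procedures at any time, one role responsible for reporting and responding to adverse events, and a four-member DSMB.

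**The concern.** The protocol uses labs as a safety check, but its rules for leaving the diet do not mention what labs may show. Section 8, item a lists acidosis and hyperlipidemia among the diet's risks. It is a fair inference, though not a statement in the protocol, that either can appear on a lab report without a symptom that the participant would mention at a check-in or write in a diet log. A participant in that position may tolerate the diet and follow it fully. Applied literally, section 4 item f would not remove that person and section 7 item d would rule out an early stop.

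At stake is the investigator's clear authority to act on a result, and a set of rules that agree with one another.

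**Working it through.** No calculation bears on this point. The check sets each possible ground for leaving the diet against the two rules and the rest of the protocol.

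| Ground for leaving | Section 4, item f | Section 7, item d | Elsewhere |
|---|---|---|---|
| Cannot tolerate the diet | Named; judged by self-report and logs | Named as the sole ground | – |
| Does not adhere | Named; judged by self-report and logs | Shut out by *only* | – |
| Participant wishes to stop | Not named | Shut out by *only* | Allowed by section 8, item b; section 4, item g also foresees ending early |
| Contraindication seen on labs | Not named | Shut out by *only* | Stated purpose of the labs (section 4 study-flow text and item h); related exclusion in section 5 |
| Severe side effect seen on labs | Not named | Shut out by *only* | Stated purpose of the labs (section 4, item h); adverse-event duty in section 8, item c |

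Three results follow.

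1. **Item d conflicts with the rest of the protocol.** Rows two and three are grounds that the protocol itself accepts and that *only* excludes. The word is wrong whatever one thinks about labs.
2. **No rule for leaving covers a lab finding.** In the last two rows, neither rule gives a ground for withdrawal. The entries in the final column give a purpose, an entry criterion and a duty to respond. None of them is a withdrawal rule.
3. **A broad reading of tolerance does not close the gap.** One could count an abnormal lab as inability to tolerate the diet. Item f stands in the way, because it names self-report and diet logs as the basis for the judgement, and a lab result is neither.

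The only number needed is the upper bound on people affected. Section 4, item a stops recruitment at 15 consented participants. The documents give no rate of contraindication or of lab abnormality, so no expected count can be given.

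**The case against.** The strongest reply is that a contraindication present at the start is an eligibility matter, and eligibility covers it. Section 5 excludes such people, and the stated purpose of the labs makes sense only if someone reads them and acts. Items f and d concern people already on the diet, so their silence on initial labs is not in itself a gap. Item d also sits in the statistics section beside a remark about interim analysis and was probably not written as a complete safety rule. The check-ins, the adverse-event duty and the DSMB lower the risk, and section 6 adds experienced diet staff for consultation.

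Much of this stands. The intention to keep contraindicated people off the diet is clear, and the point is therefore small. It does not remove the point. Item f is a procedural rule in the procedures section, and it omits a lab ground too. A result that arrives late, or a severe side effect that develops on the diet, is not settled by an entry criterion. The other safeguards do not amend either rule.

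A reader might infer three stronger things, none of which the documents support.

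- **That the diet starts before the labs are read.** Section 4, item b says "The study will last for 12 weeks for each participant" and "Participants will then return home for the 12 week diet", which seems to leave no time for review. These are rounded intervals with no visit windows, and section 4, item a speaks of "inability to travel to Baltimore for 2 study visits 3 months apart". A same-day start would be an inference. Figure 1, the study-flow diagram, is not shown and may contain a review step.
- **That the few clinical tests between the two visits measure the size of the problem.** They concern monitoring during the diet. They do not show whether the initial results are reviewed or acted on.
- **That a participant would in practice be kept on a harmful diet, or that the primary comparison is affected.** Nothing in the documents shows either.

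**Conclusion.** The point holds as a minor safety wording fix. Sections 4 (item f) and 7 (item d), as written, confine removal and early stopping to intolerance or non-adherence. They leave no ground for withdrawal on a lab-detected contraindication or severe side effect, and *only* is inconsistent with the protocol's own text. This conclusion does not depend on when the diet starts.

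The absence of a stated review of labs before the diet is a weaker, supporting observation. It is limited to the visible text and falls away if Figure 1 shows such a step; the gap in items f and d would remain.

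**What to change.** 1. In section 7, item d, delete *only*.
2. In section 4, item f and section 7, item d, add that the investigator may withdraw a participant for a contraindication or other safety finding on labs, examination or adverse-event report. What counts as a contraindication stays with the sponsor.
3. As a supporting step, state that the diet begins once the investigator has reviewed the initial-visit labs against the section 5 exclusion. If Figure 1 already says so, no change is needed here.

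The cost is a few sentences and, for step 3, one phone or e-mail message per participant, so at most 15. No extra visit, draw or test is required. Step 3 may move the return visit later by the lab turnaround, which the documents do not give. Because participants pay for their own travel (section 11), the return trip is best booked after the diet has been released. Anyone withdrawn on the new ground would fall outside the completers-only analysis in section 7, item c, as any other early leaver already does.
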